9.0 STATISTICAL CONSIDERATIONS

9.1 Sample Size and Study Duration

One disease stratum (infantile fibrosarcoma, Cohort A) has been identified as the primary cohort for reporting upon completion of evaluation. The evaluation rule is described in [Section 9.2](#) below. In addition to the main stratum, enrollment into each of the following tumor

groups (“secondary strata”): (B) Other newly-diagnosed TRK fusion solid tumors, and (C) Relapsed/refractory acute leukemias; will be open to accrual. If nine response-evaluable patients of a particular histology are enrolled in either of the secondary strata, the two-stage design described in [Section 9.2](#) below will be applied to that particular histology. (That is, up to twelve additional response-evaluable patients with that tumor type may be studied.) Upon completion of enrollment to Cohort A, the study committee will make a decision on whether to continue enrollment to the secondary strata or to close the study. This will be based on the enrollment and response rates observed in the strata up until that date.

Review of SEER data indicates the following entry rate can be expected, assuming that 33% of patients with infantile fibrosarcoma have resectable disease at diagnosis, and 33% of the remaining patients don’t enroll on this study for other reasons:

| Disease Group/Strata | Patients/Year |
|-----------------------------|----------------------|
| Infantile fibrosarcoma | 8 |

Assuming an annual enrollment rate of 8 patients/year in Cohort A, the probability of accruing 9 patients to complete the initial stage of evaluation within 17 months is 80% and within 26 months is 90%. The corresponding probability for enrolling 21 patients in 37 months is 80% and within 47 months is 90%. Allowing for a 10% inevaluability rate, a minimum of 9 and a maximum of 70 patients will be enrolled. The study will likely require 3 to 4 years for sufficient patient enrollments to evaluate larotrectinib in IFS.

Assuming all three cohorts fill completely, a maximum of 63 evaluable patients will enroll. Accounting for up to an estimated 10% of patients in Cohort A who do not meet the definition of evaluable for response and therefore require replacement, a maximum of 70 total patients will enroll.

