Larotrectinib is a highly selective oral small molecule inhibitor of the TRK family of tyrosine kinases (TRKA, TRKB, and TRKC) which are encoded by the NTRK genes (*NTRK1*, *NTRK2*, and *NTRK3*). Fusions of these genes (TRK fusions) occur across a wide range of pediatric and adult malignancies, and are nearly pathognomonic for infantile fibrosarcoma. Preclinical studies have shown that larotrectinib is active in cancer cell lines harboring TRK fusions, while having no activity in cell lines without these fusions. Ongoing clinical trials of larotrectinib in children and adults have shown a 75% centrally confirmed objective response rate in patients with relapsed or refractory TRK fusion cancers across a wide range of tumor types, including a 93% objective response rate in children with TRK fusion cancers on a Phase 1 trial. This study also established a pediatric recommended phase 2 dose. Given the remarkable activity seen in the relapsed/refractory setting, this open label two-stage phase 2 trial will enroll newly diagnosed patients with any TRK fusion solid tumor. The primary cohort will be patients with infantile fibrosarcoma, and patients with other TRK fusion solid tumors will be analyzed in a separate cohort. This study will also include an exploratory cohort for patients with relapsed or refractory TRK fusion acute leukemias, and the results of this cohort will be reported descriptively. Larotrectinib will be administered orally twice daily on a continuous dosing schedule of 28-day cycles at a dose of 100 mg/m²/dose with a maximum of 100 mg/dose. Patients with localized tumors who achieve sufficient tumor shrinkage to allow complete resection and those who achieve a complete response will discontinue larotrectinib at protocol specified timepoints and continue to be followed for recurrence. Patients who do not meet these criteria will receive 26 cycles (approximately 2 years) of therapy and then be followed for recurrence. The primary endpoint will be the objective response rate in patients with infantile fibrosarcoma. We will also evaluate event-free survival (EFS), duration of response (DOR), and overall survival (OS). These endpoints will be separately evaluated in patients with all other TRK fusion solid tumors combined. A Simon two-stage design that incorporates the best overall response within 6 months will be utilized.

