9.2 Study Design

The primary endpoint will be objective response according to the disease specific criteria in [Section 10](#). The best response of disease to larotrectinib will be examined separately in the primary disease stratum and the secondary strata if sufficient enrollment occurs. The following Simon’s minimax two-stage design will be used in each stratum.

| | Cumulative Number of Responses | Decision |
|--|-----------------------------------|---|
| Stage 1: Enter 9 patients | 5 or fewer | Terminate the trial: agent ineffective |
| | 6 or more | Inconclusive result, continue trial (proceed to Stage 2) |
| Stage 2: Enter 12 additional patients | 15 or fewer | Terminate the trial: agent ineffective |
| | 16 or more | Terminate the trial: agent effective |

We will consider larotrectinib not of sufficient interest for further evaluation in a disease category if the true response rate is 60% and of sufficient activity if the true response rate is 85%. If larotrectinib has a true response rate of 60%, the rule described above will

identify it of sufficient activity for further study with probability 9.05% (type I error), and the trial will have an expected sample size of 14.8 with 51.74% probability of early termination. If larotrectinib has a true response rate of 85%, the rule described above will identify it of sufficient activity for further study with probability 90.40% (power against the alternative hypothesis $p = 0.85$).

If there are 9 confirmed objective responses before observing any nonresponders in Cohort A, consideration of closing Cohort A to enrollment will be discussed by all approved parties (i.e., DSMC, Bayer, and CTEP) following release of the response data by the DSMC. Nine responses among the first 9 response evaluable patients will exclude a true response rate of 60% with $p = 0.014$. If at any time there are 16 confirmed responses in a cohort, then enrollment to that cohort will be closed as the efficacy endpoint for that cohort has been met.

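### Sections 9.1 and 9.2 give different units for the two-stage rule in the secondary cohorts, so Cohort B has no single decision rule

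*Combined protocol and SAP*

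**What the plan says.** Section 9.1 names the secondary strata as Cohort B (other newly diagnosed TRK fusion solid tumors) and Cohort C (relapsed or refractory leukemias). It then applies the Section 9.2 design at a finer level: "If nine response-evaluable patients of a particular histology are enrolled in either of the secondary strata", that histology gets the two-stage test, with room for twelve more patients of the same tumor type.

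Section 9.2 sets the design ("Stage 1: Enter 9 patients", then "Stage 2: Enter 12 additional patients"; 6 or more responses to continue, 16 or more to call the agent effective). It says the "minimax two-stage design will be used in each stratum". It adds a closure rule at cohort level: "If at any time there are 16 confirmed responses in a cohort", enrollment to that cohort stops because its efficacy endpoint has been met. That sentence gives no number of patients.

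Other places bear on the unit:

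- Section 9.1, total size: "Assuming all three cohorts fill completely, a maximum of 63 evaluable patients will enroll".
- Abstract: the endpoints for the other solid tumors are evaluated with those tumors combined. For leukemia, "the results of this cohort will be reported descriptively".
- Section 1.2, aim 1.2.2: response rate is to be determined for non-IFS solid tumors as one group.
- Section 9.3: confidence intervals for response rates must account for the two-stage design.

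**The concern.** In Cohort A histology, stratum and cohort are the same thing. In Cohort B they cannot be, because Section 3.2.2 admits any non-IFS solid tumor except high-grade glioma. The two sections can therefore reach different conclusions from the same Cohort B data. Suppose three histologies enroll eight patients each (an assumed mix). Under Section 9.1 none reaches nine, so neither futility nor efficacy is tested. Under Section 9.2, 16 responses among those 24 patients mean that the endpoint has been met.

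The Cohort B response rate is a named secondary aim, and its two-stage confidence interval needs a defined group, a maximum size and a stopping rule. Until the unit is settled, that interval is not defined. The error rates quoted in Section 9.2 also carry over to Cohort B only if it is treated as one group of at most 21.

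**Working it through.** **Inputs (Section 9.2).** Null rate 0.60 and target rate 0.85. Stage 1 has n1 = 9, continuing on 6 or more responses. Stage 2 adds 12, for n = 21, with success at 16 or more. Exact binomial throughout.

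**1. Reproduce the stated design.** P(success) = sum over x = 6 to 9 of P(Bin(9, p) = x) x P(Bin(12, p) >= 16 - x).

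| x in stage 1 | p = 0.60 | p = 0.85 |
|---|---|---|
| 6 | 0.2508 x 0.0834 = 0.0209 | 0.1069 x 0.7358 = 0.0787 |
| 7 | 0.1612 x 0.2253 = 0.0363 | 0.2597 x 0.9078 = 0.2357 |
| 8 | 0.0605 x 0.4382 = 0.0265 | 0.3679 x 0.9761 = 0.3591 |
| 9 | 0.0101 x 0.6652 = 0.0067 | 0.2316 x 0.9954 = 0.2305 |
| Sum (unrounded terms) | 0.0905 | 0.9040 |

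Early termination at 0.60 is P(Bin(9, 0.6) <= 5) = 0.5174. Expected size is 9 + 12 x (1 - 0.5174) = 14.8. All four stated figures reproduce.

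**2. Which unit fits the totals?** Per cohort: 3 x 21 = 63 evaluable, and 63 / 0.9 = 70 enrolled. Both match Section 9.1. Per histology, read by itself, the cap of 21 belongs to the tumor type. If two histologies filled in Cohort B (an assumption), the total would be 21 + 42 + 21 = 84, so 63 would not be a maximum.

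**3. What the 16-response wording does without a cap of 21.** The sizes 24 and 30 are assumptions; the documents give no size for Cohort B alone. The true rate is 60%. The gated column repeats the step 1 formula with n - 9 in place of 12. The ungated column is P(Bin(n, 0.6) >= 16).

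| Evaluable patients in Cohort B | Stage 1 gate kept | No gate |
|---|---|---|
| 21 | 9.05% | 9.6% |
| 24 | 25.6% | 33% |
| 30 | 45.5% | 82% |

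With the gate the probability cannot exceed 1 - 0.5174 = 48.3% at any size. The ungated column applies only if no futility look operates in Cohort B. That is what Section 9.1 implies when no single histology reaches nine.

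**The case against.** The strongest reply is that little depends on this. Cohort A carries the primary aim, and its operating characteristics stand. Cohort B response is a secondary estimate, with evaluability defined in Section 9.4. Section 2.7.1 says accrual is complete, so enrollment caps and closures can no longer act, and choosing a unit now would be a choice made with results known. All of this stands, and it shapes the fix. It does not remove the conflict, because Section 9.3 still requires an interval that respects the two-stage design.

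It can also be said that Cohort B is limited anyway, by the 63 and 70 totals and by a study committee decision once Cohort A completes. Those limits are real, so it would be wrong to call Cohort B unlimited. They bound the study and not the cohort: with Cohort A at 21 and Cohort C empty, 63 would still leave 42 for Cohort B. If larotrectinib is highly active, however, passing 21 is unlikely. At a true rate of 85%, 16 responses are expected after about 16 / 0.85 = 19 patients.

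A reader might infer that per-histology testing lets several full tests run in Cohort B and multiplies the false-positive rate. The documents do not support that. Closure at 16 responses in the cohort means one histology could reach 16 only if essentially every response came from it.

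A reader might also infer that the plan for leukemia is plainly contradictory. That part is weak. Descriptive reporting can coexist with a stopping rule, and Section 2.1.5 describes TRK fusion leukemia as rare. The text simply does not say which is meant.

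Finally, pooling is itself a design choice. Cohort B mixes CNS tumors, judged on a 50% fall in the product of two diameters (Section 10.5.2), with tumors judged on a 30% fall in one diameter (Section 10.3.3). This is a further reason to record the rule used and not to impose one.

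**Conclusion.** The concern holds for Cohort B. Sections 9.1 and 9.2 name different units, no text says which governs, and Section 9.1 does not fit its own total of 63. The phrases in Section 9.2 about sufficient enrollment and disease category do not settle it, since Section 9.1 has already defined the strata as the cohorts. The 9.05% and 90.40% figures apply to 16 of 21 in one prespecified group and to nothing else.

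The possible inflation at a true rate of 60% is to 25.6% at 24 patients and 45.5% at 30 with the stage 1 gate, or 33% and 82% without it. These are scenarios that assume Cohort B went past 21 evaluable patients; they are not forecasts. It would be wrong to infer that the primary analysis is affected. The cap of 21 for Cohort B is implied by 63 = 3 x 21 and by the design table; it is not stated in words. The point should be settled before Cohort B is reported against a decision rule.

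**What to change.** Reconcile Sections 9.1 and 9.2 to one unit for Cohort B. The reading that matches the 63 maximum, the abstract and aim 1.2.2 is the pooled cohort, capped at 21 evaluable patients. Because accrual is complete, state which rule was actually applied during enrollment, and do not select one after seeing results. Label the other level of summary, per histology or pooled, as descriptive.

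Reword the closure criterion to: *16 confirmed responses among at most 21 evaluable patients in the cohort* (naming the histology instead, if that was the unit in force). Compute the two-stage confidence interval for Cohort B on that basis. For Cohort C, state either that a stopping rule applies or that the cohort is descriptive only.

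The cost is a few sentences in Sections 9.1 and 9.2 and a check of the enrollment records to confirm the rule used. No further patients or data are needed.

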9.2 Study Design

The primary endpoint will be objective response according to the disease specific criteria in [Section 10](#). The best response of disease to larotrectinib will be examined separately in the primary disease stratum and the secondary strata if sufficient enrollment occurs. The following Simon’s minimax two-stage design will be used in each stratum.

| | Cumulative Number of Responses | Decision |
|--|-----------------------------------|---|
| Stage 1: Enter 9 patients | 5 or fewer | Terminate the trial: agent ineffective |
| | 6 or more | Inconclusive result, continue trial (proceed to Stage 2) |
| Stage 2: Enter 12 additional patients | 15 or fewer | Terminate the trial: agent ineffective |
| | 16 or more | Terminate the trial: agent effective |

We will consider larotrectinib not of sufficient interest for further evaluation in a disease category if the true response rate is 60% and of sufficient activity if the true response rate is 85%. If larotrectinib has a true response rate of 60%, the rule described above will

identify it of sufficient activity for further study with probability 9.05% (type I error), and the trial will have an expected sample size of 14.8 with 51.74% probability of early termination. If larotrectinib has a true response rate of 85%, the rule described above will identify it of sufficient activity for further study with probability 90.40% (power against the alternative hypothesis $p = 0.85$).

If there are 9 confirmed objective responses before observing any nonresponders in Cohort A, consideration of closing Cohort A to enrollment will be discussed by all approved parties (i.e., DSMC, Bayer, and CTEP) following release of the response data by the DSMC. Nine responses among the first 9 response evaluable patients will exclude a true response rate of 60% with $p = 0.014$. If at any time there are 16 confirmed responses in a cohort, then enrollment to that cohort will be closed as the efficacy endpoint for that cohort has been met.

9.3 Methods of Analysis

Response criteria are described in [Section 10.2](#). A responder is defined as a patient who achieves a best response (as defined in [Section 10.3.4](#)) of PR or CR on the study. Response rates will be calculated as the percent of evaluable patients who are responders, and confidence intervals will be constructed accounting for the two-stage design.

Toxicity tables will be constructed to summarize the observed incidence by type of toxicity and grade. A patient will be counted only once for a given toxicity for the worst grade of that toxicity reported for that patient. Toxicity information recorded will include the type, severity, time of onset, time of resolution, and the attribution(s) to the study regimen.

Time-to-event analyses (time to progression, progression-free survival, overall survival, and duration of response) will be computed one year after the last enrollment in a stratum. Duration of response will be defined among patients with a confirmed best response of either PR and CR, and will be defined as the time from the first observation of either PR or CR until either the first observation of PD (event) or last known observation of the patient (censored observation).

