1.2 Secondary Aims

- 1.2.1 To determine event-free survival (EFS), overall survival (OS), and duration of response (DoR) of children with IFS treated with neoadjuvant larotrectinib prior to local control.
- 1.2.2 To determine the ORR, EFS, OS, and DoR of children with newly diagnosed TRK fusion solid tumors other than IFS treated with neoadjuvant larotrectinib prior to local control.
- 1.2.3 To describe the toxicity of larotrectinib in children with solid tumors and acute leukemia.
- 1.2.4 To determine the percentage of patients with TRK fusion solid tumors with detectable circulating tumor DNA at baseline and after 2 weeks, 4 weeks, 24 weeks of treatment, at the time of discontinuation of larotrectinib therapy, and at progression.

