1.3 Exploratory Aims

- 1.3.1 To determine the EFS, OS, and DoR of children with TRK fusion solid tumors other than IFS treated with adjuvant larotrectinib following upfront surgery with positive margins after neoadjuvant larotrectinib.
- 1.3.2 To determine the EFS, OS, and DoR of children with TRK fusion solid tumors who experience a complete response to larotrectinib and subsequently discontinue larotrectinib therapy
- 1.3.3 To determine the remission induction rate for patients with recurrent/refractory TRK fusion leukemia when treated with larotrectinib.
- 1.3.4 To evaluate the surgical morbidity and extent of resection of initially unresectable tumors in patients with TRK fusion solid tumors who undergo surgical resection following neoadjuvant larotrectinib.
- 1.3.5 To evaluate mechanisms of response and resistance to larotrectinib in children with TRK fusion cancers.
- 1.3.6 To evaluate the morphologic features of TRK fusion solid tumors at time of initial

biopsy to further define criteria for pathologic diagnosis of these tumors.

- 1.3.7 To evaluate immunohistochemistry for pan-TRK as a screening method for TRK fusion tumors and in resection specimens following neoadjuvant treatment with larotrectinib.
- 1.3.8 To evaluate the histologic response to larotrectinib in resection specimens following neoadjuvant treatment.
- 1.3.9 To evaluate circulating tumor DNA for the detection of the emergence of resistance mutations and recurrence in patients with TRK fusion solid tumors treated with larotrectinib.
- 1.3.10 To evaluate the ratio of CSF to concurrent plasma concentrations of larotrectinib in patients with leukemia.
- 1.3.11 To evaluate the change in neurocognitive/behavioral functioning over time between baseline and 5 years post-diagnosis of patients treated on this protocol using parent-reported adaptive functioning (ABAS-III General Adaptive Composite), executive function (BRIEF-P or BRIEF-2 Global Executive Composite Score), psychosocial functioning (BASC-3 Internalizing, Externalizing and Behavioral Symptoms Indices) and quality of life (PedsQL Total score).

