The largest datasets on the therapy and outcome of children with IFS come from the European experience. A retrospective analysis of 56 infants with IFS from the years 1979-2005 has been reported, and the European pediatric Soft tissue sarcoma Study Group (EpSSG) conducted a prospective study of a standardized treatment regimen for such children from 2005-2012.^{23, 24} These studies demonstrated that most children with completely resected tumors, with or without positive margins, remain disease free without further therapy. Across both studies, only 1 of 21 Intergroup Rhabdomyosarcoma Studies (IRS) Group 1 patients, and 3 of 19 of IRS Group 2 patients who did not receive adjuvant chemotherapy suffered a relapse.^{23, 24}

Despite the good outcome with limited therapy in infants with Group 1 and 2 disease, most infants had IRS Group 3 (incompletely resected) disease (57 of 105 patients across the two series).^{23, 24} There is a significant burden of therapy in these children. The majority of children with Group 3 disease are treated with chemotherapy.²⁴ The prospective EpSSG study was conceived to attempt to reduce alkylator exposure and assess the ability to prevent morbid surgery in these patients. On this protocol, IRS Stage 3 patients were treated with vincristine and actinomycin, and alkylators and/or doxorubicin were only added if there was disease progression or insufficient tumor response to allow subsequent surgical resection. Despite this strategy, 5 of 27 IRS Group 3 patients had progressive disease, 1 suffered a metastatic relapse, 1 died of toxicity, 6 received alkylator based therapy, 3 developed venoocclusive disease (VOD), 2 underwent limb amputation, and 1 underwent extenteration.²³ The objective response rate (defined as a >33% reduction in tumor volume) to chemotherapy for these patients was 62.9% (17/27 patients). Of these 27 patients, 7 had an event (death, progressive disease, or relapse), for an estimated 74% event free survival. Thus, there is the opportunity to improve outcome and there remains a significant burden of therapy for the IRS Group 3 patients.

2.1.3 Congenital Mesoblastic Nephroma (CMN):

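### Section 9.3 omits the EFS named in the aims and leaves it undefined, and its duration-of-response rule censors a responder who dies without documented progression.

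*Combined protocol and SAP*

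**What the plan says.** The abstract states: "We will also evaluate event-free survival (EFS), duration of response (DOR), and overall survival (OS". Aim 1.2.1 reads "To determine event-free survival (EFS), overall survival (OS), and duration of response (DoR) of children with IFS", and aim 1.2.2 reads "To determine the ORR, EFS, OS, and DoR of children with newly diagnosed TRK fusion solid tumors other than IFS". Exploratory aim 1.3.1 names the same three endpoints for non-IFS patients who receive larotrectinib after surgery with positive margins. Aim 1.3.2 does so for complete responders who stop the drug: "To determine the EFS, OS, and DoR of children with TRK fusion solid tumors who experience a complete response to larotrectinib".

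Section 9.3 is the only place that sets out time-to-event analyses. Its list is "Time-to-event analyses (time to progression, progression-free survival, overall survival, and duration of response", to be computed one year after the last enrollment in a stratum. Of these, only DoR is defined there. It runs from the first PR or CR, in patients with a confirmed best response of PR or CR, until "first observation of PD (event) or last known observation of the patient (censored observation".

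**The concern.** A named secondary endpoint for both solid-tumor cohorts has no listed analysis and no definition. Whoever writes the report must decide what counts as an EFS event, when the clock starts and how patients are censored. Section 2.7.1 indicates that the trial's activity results are already known, so that choice would be made with the data in view.

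For DoR the text is explicit, and that is the difficulty. A responder who dies without recorded progression leaves the analysis as a censored case, treated as having the same future risk of progression as patients still in response. In cohorts of about 20 patients, one such death is visible in the estimate.

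**Working it through.** **1. Is EFS defined anywhere for this trial?**
- Abstract and aims 1.2.1, 1.2.2, 1.3.1, 1.3.2: EFS is named, without start date, events or censoring.
- Section 9.3: EFS is absent. TTP and PFS are listed without definition, and nothing equates either with EFS.
- Section 2.1.2, on the prospective European series: "7 had an event (death, progressive disease, or relapse), for an estimated 74% event free survival". This is an event list, but for a historical cohort. The figure reproduces: 1 − 7/27 = 20/27 = 74.1%.

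The event list matters to that benchmark. The same paragraph reports 5 progressions, 1 metastatic relapse and 1 toxic death. If these do not overlap, they are the 7 events (5 + 1 + 1). Leaving out the toxic death would give 21/27 = 77.8%, which is 3.7 points higher.

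**2. Does PD include death?** No. Section 10.3.3 defines PD by growth of at least 20% or new lesions, and Section 10.5.2 uses 25% growth or new lesions for CNS tumors. Section 9.4 names death alongside progression, but only to decide who is evaluable for response.

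**3. Direction of the effect on DoR.** In a Kaplan-Meier estimate, a death with m patients at risk multiplies the curve by (1 − 1/m) if it is an event and by 1 if it is censored. Later risk sets are the same either way. The PD-only curve is therefore never below the curve that counts deaths.

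**4. Size, by illustration.** The documents give no DoR events, so these inputs are assumptions: n responders, 2 PDs, 1 death without PD, and everyone else followed past the last event. The values of n come from Section 9.2: 21 is the full cohort (9 + 12), and 16 is the closing boundary, "If at any time there are 16 confirmed responses in a cohort, then enrollment to that cohort will be closed".
- Death as event: (n − 3)/n.
- Death censored before both PDs: (n − 3)/(n − 1).
- Death censored between the PDs: (n − 1)/n × (n − 3)/(n − 2).
- Death censored after both PDs: (n − 2)/n.

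| n | Death as event | Censored before | Censored between | Censored after | Difference (points) |
|---|---|---|---|---|---|
| 16 | 13/16 = 81.25% | 13/15 = 86.67% | 87.05% | 14/16 = 87.50% | +5.42 to +6.25 |
| 21 | 18/21 = 85.71% | 18/20 = 90.00% | 90.23% | 19/21 = 90.48% | +4.29 to +4.76 |

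**5. The primary design.** Recomputing the 5/9, 15/21 rule gives type I error 0.0905, power 0.9040, early-termination probability 0.5174 and expected sample size 14.79. These agree with Section 9.2, and none depends on EFS or DoR.

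**The case against.** The strongest reply on EFS is that PFS was probably meant. That is plausible, and it makes the defect an unreconciled name with a missing definition rather than an endpoint given up. It does not remove the defect, because PFS is undefined too and the documents never say that the two are the same.

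On DoR, one can argue that time from response to progression is a legitimate quantity with a stated rule, and that deaths still appear in overall survival. This stands as a reason to keep reporting the PD-only version. It does not make that version a good summary of how long patients remain alive and in response.

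The effect may also be small. Section 8.1 accepts clinical evidence of progression, so many deaths from disease would already be recorded as PD. Section 2.1.2 cites IFS survival of 80–100%. Both points stand.

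A reader might also infer that the censoring rule adds a fixed stretch of unassessed time after the last scan. The documents do not support a bound. Section 9.3 does not say whether the last observation means a disease assessment or any contact. Section 4.1.1 allows up to 21 days for recovery after the drug is stopped for toxicity, and Section 4.3.3 lets a cycle start late. Because progression may be declared clinically (Sections 4.3.2, 7.1 and 8.1), an examination can itself be a disease-status observation. Censoring at scans alone would be inconsistent with that.

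**Conclusion.** Both parts hold on the text. EFS is named in the abstract and four aims, has no entry in Section 9.3 and has no definition for this trial. The DoR rule, followed as written, censors death without documented PD, and this can only flatter DoR or leave it unchanged.

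The 4 to 6 points rest on one death, two progressions and 16 to 21 responders, with no other censoring. They should not be read as the bias in this trial, since the documents report none of those counts. Nor are they a limit: Section 9.2 allows discussion of closing Cohort A after 9 straight responses, and smaller cohorts shift more.

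A reader might infer that the response-rate conclusion is in doubt. It is not, because the test, sample size and error rates do not use these endpoints. This is a correction that should be made to secondary analyses, not a flaw in the main result.

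**What to change.** In Section 9.3:
- List EFS as the time-to-event endpoint for aims 1.2.1 and 1.2.2, measured from enrollment, with PD, relapse or death from any cause as events. State a separate time origin for the subsets in aims 1.3.1 and 1.3.2.
- Censor EFS at the last disease-status assessment, meaning imaging, or a clinical assessment where the protocol accepts clinical progression.
- Replace TTP and PFS with EFS, or keep them with definitions and a sentence on how they relate to it.
- Count death from any cause as a DoR event, and report the PD-only DoR as now written beside it.
- Label both changes as made after accrual and after results were reported. Section 2.7.1 says accrual is complete and activity has been demonstrated, and cites a report of this trial.

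The cost is analysis text and a rerun. Disease evaluations are already scheduled in Sections 7.1 and 7.2, and death is an off-study criterion in Section 8.2, so no new visits should be needed. The case report forms are not in the documents, so the availability of the dates should be confirmed. The downside is that DoR may become slightly less favourable and the change is post hoc.
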